Following the two weeks of CREMA data collection, a laboratory session will be conducted to investigate responses to acute dosing of oxytocin (versus placebo) in context of controlled evaluation of stress reactivity and smoking behavior. Prior to the session, participants will abstain from smoking for 12 hours and provide a salivary sample for measurement of stress and sex hormone (cortisol, estradiol, progesterone, and testosterone) levels. Participants will receive a double blind intranasal dose of oxytocin or placebo and will then be exposed to the Trier Social Stress Test (TSST). Measures collected at multiple time points during the laboratory session will include subjective craving, stress, and negative emotion as well as heart rate, blood pressure, skin conductance, and cortisol. Immediately following the TSST, participants will complete a smoking resistance task (SRT) in which they will receive a monetary reward for every 5-min period they can resist smoking. After completing the SRT, participants will be allowed to smoke freely during a one-hour ad libitum smoking period (ASP), with smoking topography assessed via a portable device.

Aim 1: Evaluate gender and sex hormone influences on reactivity to stressful and smoking-related cues presented, via CREMA, in the natural environment of smokers.

Hypothesis 1: Female smokers will be more reactive (craving ratings) than male smokers to stressful and smoking-related cues presented in the natural environment.

Hypothesis 2: Among female smokers, estrogen to progesterone ratio will be positively related to reactivity (craving ratings) to stressful and smoking-related cues presented in the natural environment.

Aim 2: Evaluate gender, sex hormone, and oxytocin administration influences on stress, craving, and smoking behavior response to a laboratory-based stressor task (TSST).

Hypothesis 1: Female smokers will evidence greater subjective stress, craving, and smoking behavior (e.g., shorter latency to smoke during the SRT and greater number of puffs during the ASP), but less neuroendocrine reactivity (cortisol), to the TSST than male smokers.

Hypothesis 2: Oxytocin, relative to placebo, will attenuate subjective stress, craving, and neuroendocrine responses to the TSST.

Hypothesis 3: Among female smokers, estrogen to progesterone ratio will be positively related to craving reactivity during the TSST.

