A goal of our ongoing SCOR study is to more directly investigate the relationship between ovarian hormones and smoking behavior. Within this study, we examined the predictive relationship between static and dynamic plasma levels of estradiol and progesterone and (a) craving elicited in a human laboratory cue reactivity procedure, and (b) smoking behavior during a subsequent 1-hour ad libitum smoking session. Briefly, 93 female smokers received an initial assessment to determine study eligibility, nicotine dependence severity, etc. Approximately one week later, participants were administered a standardized cue reactivity assessment where the Questionnaire of Smoking Urges–Brief (QSU-B) was used to measure craving prior to and after exposure to smoking-related cues (i.e., preferred brand of cigarette & lighter). An ad libitum smoking session followed, with measurement of smoking behavior via a topography device. Estradiol and progesterone levels were derived from plasma samples collected at the time of the initial assessment (T1) and the laboratory cue reactivity assessment (T2). The primary predictor variables were absolute levels of estradiol and progesterone at T2, % change in estradiol and progesterone between T2 and T1; primary craving reactivity outcomes were QSU-B factor and total scores (difference score = postcue - precue craving) and primary ad libitum smoking outcomes were number of puffs and weight of cigarettes smoked.

[figure not shown]
Cue reactivity analyses indicated that the ratio of estradiol to progesterone correlated positively ($p < .05$) with QSU craving. While not significant in magnitude within the preliminary sample, the direction of association was positive for estradiol (T2 level and % change between T1 and T2) and negative for progesterone measures (T2 level and % change between T1 and T2). Ad libitum smoking analyses revealed a similar pattern of findings. While directional trends existed in static and dynamic hormone associations with smoking variables, only the ratio of progesterone to estradiol significantly predicted number of puffs ($p < .01$) and weight of cigarettes ($p < .05$) smoked. These findings are among the first to suggest that the smoking behavior of women may be

influenced by the relationship between estradiol and progesterone rather than by the effects of progesterone alone, as suggested by at least two previous laboratory studies (Sofuoglu, et al., 2001; Sofuoglu, et al., 2011).

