A total of 250 smokers, between the ages of 18-45, will be recruited over a 51-month period. The oversampling of female participants was necessary to achieve adequate power to test hypotheses involving ovarian hormone measures. The sample size determination was based on statistical power necessary to test primary hypotheses as outlined in the Sample Size Determination, Section C3i, below.

Participants will be recruited from the general community through media advertising (radio, print, online and television). Advertisements will target smokers interested in participating in a study examining the relationship between stress and smoking. This media-based recruitment strategy has generated large numbers of participants for both cessation and non-cessation studies. To illustrate, we have an ongoing cessation study for women smokers that attracted 400 screening calls and netted 46 study enrollees over a 12-month recruitment period. Respondent-Driven Sampling (RDS) will also be used to enhance recruitment of the sample. The RDS sampling methodology is based on recruiting the eligible friends and acquaintances of each participant so that the sample “snowballs”. Each eligible participant who is randomized into the study, and agrees to take part in this recruitment assistance, will be given business cards to pass on to other potential participants. The business cards will have a unique code linked to the person who passes them out. A referral will be instructed to call the site offices for screening and, if eligible, an appointment for further evaluation. If a referral completes the screening process and is eligible for the study, the participant who referred the person can redeem the business card for \$20.

Since the proposed study targets both female and male smokers who are not currently interested in quitting, we anticipate successfully recruiting at least 2-3 female and 1-2 male smokers per month using our aggressive recruitment strategies. This rate of recruitment will allow us to achieve our target sample over the 51-month recruitment period. Inclusion/exclusion criteria for the study are located in the Protection of Human Subjects section of this application.

C3c. Intake and Comprehensive Assessment.

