This study is powered to test the hypothesis that non-cigarette-deprived females will be more reactive to smoking cues than males, as measured in the natural environment of smokers via CREMA technology. However, the sample size obtained for this is adequate to test all the four hypotheses with at least 80% power. The justifications for the power calculations are as follows. A recent study (Heishman, et al., 2010) found that non-cigarette-deprived females responded to smoking cues with 10% greater craving than males (i.e., 10-unit difference on a 100-mm VAS), with this difference corresponding to an effect size of $d = 0.7$. Since the proposed design intends to assess gender differences in a non-laboratory setting, we have reduced the expected effect size by 30% to 0.50. Based on the four-item subscale of the QSU (cf., Warthen & [name], 2009b) to be used in the proposed study, a comparable detectable gender difference would be 0.45 ($sd=0.9$). Accounting for the multiple correlated measures within each participant (i.e., reactivity will be measured multiple times daily for 14 days using CREMA) through a between-observation correlation (autocorrelation) of 0.70, a sample of 96 females and 48 males is necessary to achieve 90% power (with a two sided type I error rate of 0.05) to detect the minimum relevant effect size of $d=0.50$. It is estimated that up to 20% of the participants may be lost before completion of the study.

Assuming 144 participants complete all study procedures (accounting for 20% dropout), we will also have 80% power with a type I error of 0.05 to detect a minimum effect size of $d=0.50$ between females and males in stress and craving response to the TSST and similarly between the oxytocin and placebo groups.

C3j. Data Management & Statistical Analysis.

Data Management

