menses. Linear models may thus be inappropriate. Traditional analyses group the hormone curves based on the estimated phases of women's menstrual cycle (follicular and luteal) for the analyses. In addition to performing the data analyses using the same method, analysis will be extended to incorporate the non-linear patterns of an individual's hormone profile. This method will be based on a non-linear regression model that has two to three segments, each one of which may be either quadratic or linear (Marrie, Dawson, & Garland, 2009). The 'joint-points' at which the segments meet, which are referred to as knots, will also be treated as unknown and determined through the modeling process. After identifying the segments, regression models assessing hormone measures against the outcome (e.g., cue-elicited craving) in each segment will be assessed and the results interpreted accordingly.

Aim 2: Hypotheses 1 and 2 - To test for gender and medication (oxytocin versus placebo) effects on reactivity profiles to the TSST during the laboratory session, a linear mixed effects model in which the dependent variables of interest are craving, stress and neuroendocrine (cortisol) response, and the primary independent fixed effects are gender, treatment group, and a random subject effect will be utilized. To account for the repeated measures, a covariance pattern for the error structure (such as an AR(1)) will be considered. The primary goal of this analysis will be to determine if the response to TSST is significantly different between females and males and/or significantly different between those who received oxytocin versus placebo (main effects of gender and medication). Additionally, as a secondary analysis, the interaction between gender and medication condition will be explored.

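### C3i's blanket claim of at least 80% power is not supported for the two ovarian-hormone hypotheses; with its 96 women, Aim 2 Hypothesis 3 reaches 80% only for a correlation of about 0.28 or more

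*Combined protocol and SAP*

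**What the plan says.** The Specific Aims list two hypotheses under Aim 1 and three under Aim 2. Two of the five concern ovarian hormones in women. Aim 1 Hypothesis 2 relates the estrogen to progesterone ratio to craving after cues in daily life. The other is "Hypothesis 3: Among female smokers, estrogen to progesterone ratio will be positively related to craving reactivity during the TSST".

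C3i sizes the study on the gender difference in cue-elicited craving (Aim 1 Hypothesis 1). At d=0.50, "a sample of 96 females and 48 males is necessary to achieve 90% power" ("with a two sided type I error rate of 0.05"). It then says that "the sample size obtained for this is adequate to test all the four hypotheses with at least 80% power" and offers justifications. Beyond the primary contrast, these amount to one sentence: 144 completers give 80% power for d=0.50 between women and men in stress and craving response to the TSST, and similarly between oxytocin and placebo.

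C3b says the oversampling of women was "necessary to achieve adequate power to test hypotheses involving ovarian hormone measures" and points to C3i for the sample-size basis. C3b gives a recruitment total of 250. Section 1.1 (Human Subjects Involvement and Characteristics) gives 120 women and 60 men, 180 in all.

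The hormone-craving evidence is in C1. In a study that began with 93 women, "the ratio of estradiol to progesterone correlated positively" with craving reactivity, at p<.05. No correlation, exact p-value or number analysed is given.

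**The concern.** A power figure for a mean difference between two groups does not carry over to a regression of craving on a hormone ratio in women only. That test uses 96 people rather than 144 and needs an effect size of its own. C3i supplies none for either hormone hypothesis, yet the claim of at least 80% appears to include them and C3b presents the sex ratio as chosen for them. Latency to smoke, an example outcome within Aim 2 Hypothesis 1 with its own survival model in C3j, has no power figure either.

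The risk lies in interpretation. If a hormone or latency test comes out null, the protocol would allow it to be presented as a well-powered negative finding when nothing in the document shows that it was.

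**Working it through.** **Inputs.** 96 female and 48 male completers, two-sided alpha 0.05, d = 0.45/0.9 = 0.50, correlation 0.70 between repeated measures, 20% loss (all C3i); pilot of 93 women, p<.05 (C1); recruitment of 250 (C3b) or 180 (section 1.1). For 80% power, 1.960 + 0.842 = 2.802.

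**1. The plan's own figures reproduce.**
- TSST, gender: standard error of d = √(1/96 + 1/48) = 0.1768; Φ(0.50/0.1768 − 1.96) = Φ(0.868) = 80.7% (80.2% by noncentral t).
- TSST, oxytocin, 72 v 72: √(2/72) = 0.1667; Φ(3.00 − 1.96) = 85.1%.
- Primary contrast: averaging m exchangeable measures multiplies the variance by (1 + (m−1)×0.70)/m. With m=5 this is 0.76 and power is 90.05%; with m=56 it is 0.705 and power is 92.0%.
- Recruitment: 144/0.8 = 180, which agrees with section 1.1 and not with C3b.

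**2. What 96 women can detect in Aim 2 Hypothesis 3.** Fisher z, one predictor: smallest r = tanh(2.802/√(96−3)) = tanh(0.2905) = 0.283.

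**3. Power at effects the protocol contains.** Power ≈ Φ(atanh(r)×√(n−3) − 1.96).
- C3i's only effect size, d=0.50, converted for equal groups: r = 0.5/√(0.25 + 4) = 0.243. At n=96: 0.2475×9.644 = 2.387; Φ(0.427) = 66.5%.
- Pilot at exactly p=.05 with 93 analysed: t = 1.986, r = 1.986/√(91 + 1.986²) = 0.204. At n=96: Φ(0.035) = 51.4%.
- Pilot p at which 80% would be reached: r = 0.283 in 93 women gives t = 2.81, p of about .006.

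**4. The larger target.** 250×0.8 = 200 completers; if two thirds are women (assumed, since C3b gives no split), about 133.

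| r | 96 women | 133 women |
|---|---|---|
| 0.204 | 51% | 65% |
| 0.243 | 67% | 81% |
| 0.283 | 80% | 91% |

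**5. Detectable effects for the other tests, 96/48 completers, 80% power.**
- Gender at the TSST: 2.802×0.1768 = 0.50.
- Oxytocin: 2.802×0.1667 = 0.47.
- Gender and latency: HR = exp(2.802/√((2/3)(1/3)D)). If all 144 smoke within the task, exp(2.802/√32) = 1.64. If 70% do (an illustrative assumption), D=101 and HR = 1.81.

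No comparable figure can be computed for Aim 1 Hypothesis 2. It uses repeated daily measures within women, and the protocol gives neither the variance components nor a slope.

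**The case against.** - **The sample may be larger than 96 women.** This stands in part. At 250 recruited, r=0.24 would have about 81%. But C3i rests its claim on 144 completers, so the claim fails at the sample it cites, and the two totals have to be reconciled before either figure can be used.
- **The hypothesis is directional.** A one-sided test at r=0.243 and 96 women gives Φ(2.387 − 1.645) = 77%. C3i specifies two-sided testing, and 77% is still short of 80%.
- **The pilot implies low power.** A reader might infer a definite power of about 51% to 75% by taking the pilot p to lie between .01 and .05. The documents do not support this. A result reported as p<.05 sets only a lower limit on r, the number analysed is not stated, and p<.01 belongs to number of puffs. The pilot also used plasma hormones and smoking cues, whereas this study uses saliva and the TSST.
- **Four hypotheses against five.** A reader might call this a counting error. It could equally mean four besides the primary one, or the four analysis blocks in C3j, which takes Aim 2 Hypotheses 1 and 2 together. The point does not depend on it: any four of the five include at least one hormone hypothesis.
- **Multiplicity.** In C3j "the dependent variables of interest are craving, stress and neuroendocrine (cortisol) response", tested for gender and for medication. A reader might infer that a 0.05 error rate and 80% power cannot both hold for Aim 2. C3i states 0.05 per comparison and never claims family-wise control, and the planned repeated-measures model may have more power than a single-measurement test. Requiring one primary outcome with a fixed testing sequence would be a redesign, and correcting the power statement does not call for it.

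**Conclusion.** The concern holds as a missing justification. It is not an arithmetic mistake: every calculation that C3i presents reproduces. The blanket figure of at least 80% is undemonstrated for Aim 1 Hypothesis 2 and Aim 2 Hypothesis 3. For the latter, at C3i's own sample and its only effect size, power is about 67%, and 80% requires r of about 0.28. If the true correlation matched a pilot p just under .05 in 93 women, power would be about 51%.

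These figures assume 96 female completers, a two-sided 0.05 test, a single hormone predictor and no missing saliva data. The 67% also treats d=0.50 as a fair stand-in for a hormone effect, which the protocol does not say. The threshold of r=0.28 does not depend on that or on the pilot. The documents do not show that the hormone hypotheses are underpowered; they show that adequate power was asserted and not established.

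**What to change.** 1. Reconcile the totals of 250 (C3b) and 180 (section 1.1), and state the expected female and male completers.
2. Delete the blanket sentence in C3i and name the hypotheses that the sample was sized for.
3. Give the effect detectable with 80% power for each of the others. With 96 female and 48 male completers these are d=0.50 for gender and about 0.47 for oxytocin at the TSST, r of about 0.28 for Aim 2 Hypothesis 3, and a hazard ratio of about 1.6 for latency if everyone smokes, larger if fewer do. For Aim 1 Hypothesis 2, either state the variance assumptions and calculate, or say that no power is claimed.
4. Label the hormone and latency tests secondary or exploratory unless effects of that size can be justified, and align the oversampling sentence in C3b.

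The cost is wording and a less favourable power statement. No participants are added and no procedure changes.

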Gender and Cessation Outcome: Epidemiological data (Giovino, 2002) indicate that smoking rates of both men and women have substantially declined from their peak levels in the 1960s but the rate of decline in women has been half that observed for men (25% vs. 50% rate reduction, respectively). Additionally, lower rates of cessation in women have been reported in studies of self-quitters (Fortmann & Killen, 1994; Husten et al., 1997; Ward, Klesges, Zbikowski, Bliss, & Garvey, 1997), smokers in large population-based treatment trials (Bjornson et al., 1995; COMMIT, 1995), and smokers in medication and nicotine replacement trials (Davis et al., 1994; Killen, Fortmann, Newman, & Varady, 1990; Perkins & Scott, 2008; Scharf & Shiffman, 2004; Wetter, Fiore, et al., 1999; Wetter, Kenford, et al., 1999). Thus, several studies of self-quitters and treatment-seekers echo the epidemiological data and collectively they suggest that women are less able to quit smoking than men, either alone or with the aid of treatment. Since the health and economic costs of smoking are so great, it is vital that the tobacco research community focus on the elucidation of factors that contribute to gender differences in cessation. Such efforts could inform the development of tailored interventions that strategically address gender-specific needs of smokers. The focus of this proposal will be to build upon our recent laboratory findings to (1) undertake the first prospective evaluation of gender and dynamic sex hormone influences on cue-responsive craving in the “real world” environment of smokers (i.e., outside the laboratory), and (2) evaluate the acute effects of a gender-relevant pharmacological intervention (oxytocin) targeting stress-induced craving and smoking behavior.

Conceptual Underpinnings of the Proposed Study: Smoking cessation is an important health outcome that is complex and multiply determined. Figure 1 depicts a conceptual model of several important causal variables that contribute to variation in smoking behavior, including cessation. The figure characterizes gender, and the sex hormones that impact gender, as a smoker attribute that provides the larger context for the operation of

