Relevant Gender Differences Experience. In one of our previous SCOR studies ([name] et al., in press) we examined the effects of gender on craving and cue reactivity. We recruited female (n=37) and male (n=53) nicotine dependent smokers to participate in a multi-session laboratory study of craving and cue reactivity to smoking and stress/negative affect cues. The smoking cues consisted of a package of the participant’s preferred brand of cigarettes, which (s)he held and manipulated for 90 sec. as instructed by research staff. The stressful/negative affect cues consisted of a detailed description of a recent life event that the participant perceived as emotionally negative and stressful. Neutral control cues for the smoking cues consisted of a similar guided manipulation of a pack of pencils and an eraser while a script of a neutral or relaxing event that the participant had recently experienced served as a control for the stressful/negative affect script. Following each cue presentation, participants provided subjective ratings of stress, craving, arousal (calm vs. aroused), valence (pleasant vs. unpleasant; lower ratings indicate more unpleasant) and dominance (feeling in control vs. feeling out-of-control/submissive; lower ratings indicate feeling more out-of-control/submissive). In addition to subjective

measures, heart rate (HR) and skin conductance (SC) measures of physiological arousal were assessed at baseline and during each cue exposure. ANCOVAs were performed to assess gender differences in cue reactivity; covariates in the models were responses to neutral cues, FTND score (measure of nicotine dependence level) and order of cue presentation. Results of analyses performed on smoking cue data indicated that although women trended toward having greater stress, craving, arousal, and lower valence and dominance ratings than men, none of the differences reached significance (e.g., arousal difference, $p = .09$). Analyses of the HR/SC data indicated that (a) women trended towards greater heart rate than men ($p = .05$) but this effect was not cue specific (i.e., did not vary across smoking vs. neutral cue type), and (b) SC level

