All paper-based assessments will be entered into SPSS databases using dual data entry methods for 20% of cases. Semi-annual database management and data integrity audits will be conducted. Hormone and cortisol data will be obtained from MUSC's CTSC in pre-formatted data files. HR and SC data will be acquired via specialized software and hardware (Biopac Systems, Inc.) interfaced with a computer. Standardized file formats will facilitate the rapid determination of summary values to be used for analysis purposes. The CREMA data will be automatically uploaded to a server on a daily basis and will be stored in a standard file format (to be determined in collaboration with [name] (Founder of Slicker Interactive & CREMA software developer). All data will be de-identified using participant ID number.

Statistical Analysis

Univariate descriptive statistics and frequency distributions will be calculated for all variables. Departures from distributional assumptions for the proposed parametric methods will be identified and appropriate transformations of the data will be applied or alternative procedures (semi/non parametric methods) will be employed. Baseline values for demographic, clinical, and other prognostic variables will be compared for imbalance across gender and treatment groups. These analyses will identify potential confounding variables to be used as covariates in subsequent analysis.

Aim 1: Hypothesis 1 - To test the overall hypothesis that females will be more reactive than males to stressful and smoking-related cues presented in the natural environment, a linear mixed effects model will be employed. The dependent variable will be craving and the primary independent variable will be gender. In the modeling process, within-subjects factors of stimulus type (active and neutral cues) and presentation order will also be included.

Hypothesis 2 - To test the hypothesis that the estradiol to progesterone ratio will be positively related to cue-elicited craving in the natural environment, salivary hormone levels and craving in response to the CREMA picture cues will be assessed over 14 days. Hormone curves do not behave in a linear fashion, but may, in the example of progesterone, behave in a quadratic fashion preceding menses and a linear fashion following

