To test the hypothesis that females will have a shorter latency to return to smoking than males, a discrete analog to the Cox proportional hazards model will be used. A complementary log-log model for interval censored survival times will be employed (Allison, 1982; Prentice & Gloeckler, 1978) that will take into account the interval nature of the time frame within which the return to smoking occurs. Also considered will be standard Cox proportional hazards models to compare time to begin smoking. Puff intensity, flow rate, and number of puffs will be assessed using a topography device as participants smoke freely for 1 hour following the smoking resistance task. Longitudinal data analytic methods will be applied to the craving, stress and cortisol data obtained during the laboratory session for all time points before and after the TSST.

Hypothesis 3 - To test the association between the estrogen to progesterone ratio and laboratory stress reactivity in women, a linear model will be developed to assess the relationship between hormones and subsequent stress reactivity. The dependent variables of interest will be the craving, stress and neuroendocrine (cortisol) response to the TSST while the independent variables will include the change in the hormone ratio over the week preceding the lab visit as well as the hormone ratio on the day of the visit. Assumptions such as linearity of the relationship between the hormones and reactivity measures, homoscedasticity, and normality of the error distribution will be assessed and variables will be transformed as necessary.

C3k. Operational Plan and Research Timetable.

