This application proposes a combined naturalistic and laboratory approach to investigate gender, sex hormone, and oxytocin influences on cue-responsive craving and smoking behavior. Inclusion/exclusion criteria are outlined above.

5.2 Trial Management.

The study will be managed from the Division of Clinical Neuroscience within the Department of Psychiatry and Behavioral Sciences at the Medical University of South Carolina. The target population is described above in the inclusion/exclusion criteria.

5.3 Data Management and Analysis.

Data will be entered by research assistants directly into a computer using standard database software. The data analysis plan is outlined in the Data Management & Statistical Analysis section.

5.4 Quality Assurance.

[name] (PI) and [name] (Lead Co-I), will have weekly meetings with the research assistants to discuss qualitative comments received during data collection and any problems in data collection. The statistician will periodically examine the database to look for irregularities. Initial data analyses will examine distributions of variable scores, and comparability of baseline characteristics across conditions in case analyses need to be adjusted for these. Confidentiality protections are outlined above.

5.5 Regulatory Issues.

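### Covariates are chosen by observed baseline imbalance across gender and treatment, which can waste precision in the oxytocin comparison and can adjust away part of the gender effect

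*Combined protocol and SAP*

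**What the plan says.** The rule is in C3j, Statistical Analysis, ahead of the aim-by-aim models: "Baseline values for demographic, clinical, and other prognostic variables will be compared for imbalance across gender and treatment groups". The next sentence gives the purpose: "These analyses will identify potential confounding variables to be used as covariates in subsequent analysis". Section 5.4 (Quality Assurance) repeats the idea, with early analyses to examine "comparability of baseline characteristics across conditions in case analyses need to be adjusted for these".

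The models themselves name few terms. For Aim 1, Hypothesis 1, gender is the primary predictor and "within-subjects factors of stimulus type (active and neutral cues) and presentation order will also be included". For Aim 2, Hypotheses 1 and 2, "the primary independent fixed effects are gender, treatment group, and a random subject effect will be utilized". Craving, stress and cortisol from the laboratory session are to be analysed longitudinally "for all time points before and after the TSST", but no pre-dose value is named as a covariate. Observed imbalance is therefore the only stated route by which a further between-person covariate enters.

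By contrast, the team's earlier gender study, described in C1, reports a short and specific set: "covariates in the models were responses to neutral cues, FTND score" and cue order. That is background, not part of this plan.

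**The concern.** The two contrasts need different covariate reasoning, and the rule treats them alike.

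Oxytocin is randomised (C3a). A baseline difference between arms is then a chance event and says nothing about which variables predict the outcome. Choosing covariates by imbalance takes up variables by accident and can omit the most useful one. The Laboratory Procedure Timeline in C3f already collects craving, mood and stress, and cortisol at Baseline 1, before dosing.

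Gender is not randomised, so considering confounders is proper. But the protocol's conceptual model (Section A) treats gender "as a smoker attribute that provides the larger context for the operation of" the other determinants of smoking. The baseline battery in C3g includes daily hassles, childhood adversity, distress tolerance, perceived stress, anxiety, depression and adult trauma. Several are plausible routes by which gender affects stress-related craving. If they differ by gender, the rule nominates them as confounders. Adjusting for them turns the hypothesis that women react more into a question about a direct effect that bypasses those routes. The gender conclusion would then depend partly on which scales happen to differ in the sample.

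**Working it through.** **Inputs from the documents.** C3i: 96 women and 48 men complete, d = 0.50, two-sided 0.05, 80% power for the TSST gender and oxytocin comparisons, 90% for the CREMA gender comparison. C3a: about half of each gender receives oxytocin, so about 72 per arm.

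**Assumed inputs.** The documents give no correlation between baseline and response and no gender gap on any scale, so both are shown as ranges.

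**Stated power.** Two-sample t test, noncentrality = d / (SD × √(1/n₁ + 1/n₂)).
- TSST gender: 0.5/√(1/96 + 1/48) = 2.83, power 80.2%. This matches the stated 80%, with almost no reserve.
- Oxytocin: 0.5/√(2/72) = 3.00, power 84.6%. The stated 80% is met as a floor.

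A normal approximation gives 80.7% and 85.1%.

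**Oxytocin, prespecified covariate.** Residual SD = √(1 − r²).

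| r (assumed) | Residual SD | Power, d = 0.50 |
|---|---|---|
| none | 1.000 | 84.6% |
| 0.3 | 0.954 | 87.8% |
| 0.5 | 0.866 | 93.1% |
| 0.7 | 0.714 | 98.7% |

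At d = 0.40, power is 66.4% unadjusted and 78.6% at r = 0.5.

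**Oxytocin, covariate used only if imbalanced.** Simulation with 72 per arm, one covariate and an assumed p < 0.05 screen. For r = 0.3, 0.5 and 0.7:
- Power with the screen: 84.9%, 85.3%, 86.2%.
- Power when always adjusted: 87.6%, 92.7%, 98.6%.
- Type I error with the screen: 4.8%, 4.4%, 3.6%.

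The screen took up the covariate in about 5% of runs, so nearly all the gain is lost. The error rate is conservative, not inflated.

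**Oxytocin, if change scores are the comparator.** Change-score SD = √(2 − 2r).
- d on the post-dose scale: at r = 0.7 the SD is 0.775 and power is already 97.0%, so adjustment to 98.7% adds under 2 points. At r = 0.5 the SD is 1.000 and power is 84.6%, against 93.1% adjusted.
- d on the change scale: adjustment lifts 84.6% to 93.1% at r = 0.5 and to about 90% at r = 0.7.

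**Gender at the TSST, adjusting for a pathway variable.** With gender gap g (SD) and within-gender correlation r, the adjusted effect is 0.50 − g × r and the residual SD is √(1 − r²), at 96/48.

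| g | r | Adjusted effect | Residual SD | Power |
|---|---|---|---|---|
| – | – | 0.50 | 1.000 | 80.2% |
| 0.1 | 0.5 | 0.45 | 0.866 | 83% |
| 0.2 | 0.3 | 0.44 | 0.954 | 74% |
| 0.3 | 0.3 | 0.41 | 0.954 | 68% |
| 0.5 | 0.5 | 0.25 | 0.866 | 37% |

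Allowing also for the correlation between gender and the scale takes the last row from 36.8% to 35.2%. In the 0.1/0.5 row the precision gained outweighs the effect removed, but the estimate still answers a different question.

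**The case against.** **No test is named.** C3j says variables are compared, not tested. It gives no threshold and calls the results potential confounders. This stands. A reader might infer a 5% significance screen with automatic entry, but the documents do not say so; the 5% screen above is an assumption used only to size the loss.

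**No pathway variable is named as a covariate.** This also stands. A reader might infer that the gender effect will be adjusted away. The text supports only that it can be, because nothing excludes those scales. The fall to 37% is the severe end of the range, not an expected result.

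**Pre-TSST values are already in the longitudinal data.** Largely fair. Comparing adjustment with a purely post-dose analysis shows the largest gain, and the plan does not describe a purely post-dose analysis. But Aim 2 defines its target as main effects of gender and medication, so use of the pre-dose value as a baseline is not assured.

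**The randomised comparison stays valid.** Correct. A reader might infer bias, inflated type I error or an inadequate sample size for oxytocin. None follows: simulated error was below 5%, and unadjusted power at d = 0.50 exceeds the stated 80%.

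**Any covariate in the gender model is open to the same criticism.** This has force for FTND and cigarettes per day. The Specific Aims link stress, craving and smoking behaviour to gender differences in nicotine dependence, so dependence may itself be downstream of gender. It argues for a minimal main model, not for selection by imbalance.

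**Conclusion.** The concern holds in a limited form: the stated rule selects covariates on the wrong criterion for both contrasts, and nothing elsewhere in the plan corrects it.

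For oxytocin the loss is efficiency only: roughly 3 to 14 points of power at d = 0.50 (84.6% against 87.8–98.7% for assumed r of 0.3–0.7), and under 2 points at r = 0.7 if change scores are used and d is on the post-dose scale. It matters more for effects below 0.50.

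For gender the issue is what is being estimated. Depending on which scales differ and how strongly they relate to craving, TSST power could lie anywhere from about 83% to 37% over the assumed range, against 80% unadjusted. The direction of the problem follows from the text; its size rests entirely on assumed gaps and correlations.

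**What to change.** Delete selection by imbalance from C3j and the matching phrase in 5.4, and keep baseline comparisons descriptive. Then prespecify covariates separately:

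- **Oxytocin:** the pre-dose Baseline 1 value of the outcome, and gender; FTND optional. State that Baseline 2, taken after dosing, is not a covariate. If the repeated-measures model is kept, say how Baseline 1 enters it.
- **Gender (CREMA and TSST):** a minimal main model, for example age. Exclude stress, mood, anxiety and trauma scales, and analyse them only as possible mediators. Report models that add FTND and cigarettes per day as sensitivity analyses only.

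Section 5.9 places the unblinded final analysis after all participants finish, so the lists can be fixed before then; for gender, which is not blinded, they should be fixed before outcomes are tabulated by gender. The cost is analysis-plan wording and a few degrees of freedom. Every variable is already collected.
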